The Sonavex feasibility clinical trial will be conducted in accordance with International Conference on Harmonization Good Clinical Practice (ICH GCP), and applicable United States Code of Federal Regulations (CFR). The Principal Investigator will assure no deviations or changes to the protocol take place without prior agreement from Sonavex, the sponsor, and documented approval from the Institutional Review Board (IRB), except where necessary to eliminate an immediate hazard(s) to the trial participants. All personnel involved in the conduct of this study have completed Human Subjects Protection and ICH GCP Training.

The protocol, informed consent form(s), and all participant materials will be submitted to the IRB for review and approval. Approval of both the protocol and the consent form must be obtained prior to participant enrollment. Amendments to the protocol will require review and approval by the IRB before any changes are implemented to the study. All changes to the consent form will be IRB approved; a determination will be made regarding whether a new consent needs to be obtained from participants who have previously provided consent.

1. ABBREVIATIONS

Abbreviation	Definition
AE	Adverse Event
CEC	Clinical Events Committee
CFR	Case Report Form
CKD	Chronic Kidney Disease
CPU	Central Processing Unit
DSMB	Data Safety Monitoring Board
ESRD	End-Stage Renal Disease
FDA	Food and Drug Administration
GLP	Good Laboratory Practices
GMP	Good Manufacturing Practices
ICH	International Conference on Harmonization
ICH GCP	International Conference on Harmonization Good Clinical Practice
IRB	Institutional Review Board
PHI	Personal Health Information
PI	Principal Investigator
QC	Quality Control
RVT	Registered Vascular Technologist
SAE	Serious Adverse Event
SOC	Standard of Care

Abbreviation		Definition							
SOP		Standard Operating Practices							
UADE		Unanticipated Adverse Device Effect							
US		United States							
2. PROTOCOL	SUM	MARY							
STUDY TITLE	Prospe EchoS	ctive Feasibility Study Evaluating EchoMark LP Placement and ure Measurements for Subjects Requiring Arteriovenous Fistulae.							
INVESTIGATIONAL Device	EchoN markir	EchoMark LP is a bioresorbable implant used as ultrasound marker for marking an arteriovenous fistula.							
	The Ed EchoS of arte EchoN	The EchoSure System for AVF is a diagnostic ultrasound system. EchoSure and its transducer are intended for use in clinical examinations of arteriovenous fistulae and other blood vessels that are marked with an EchoMark LP implant.							
	As a symmetry flow rational first first the second	ystem, EchoMark and the EchoSure System for AVF provides rements and information about blood flow, including volumetric ate, diameter, and depth, for assessing upper arm arteriovenous e throughout the maturation period.							
OBJECTIVES	To evaluate the feasibility and safety of the EchoMark LP and the EchoSure diagnostic ultrasound system for assessing AV fistula blood flow, diameter and depth.								
STUDY DESIGN	Prospe	ective, multi-center, single-arm, non-blinded feasibility clinical tria							
SUBJECT Populations	Subjec creation	ects undergoing new upper arm autologous arteriovenous fistula ion who require hemodialysis							
NUMBER OF Subjects	Up to 2 up to 3	to 20 subjects will be enrolled for up to 365 days. Each site can enroll o 3 "roll-in" subjects. Roll-in subjects will be consecutive and must							

	be identified as roll-in subjects prior to the EchoMark LP implantation and will not count toward the total enrollment of 20 subjects.										
NUMBER OF Clinical Sites	Up to 6 sites within in the United States will be evaluated, qualified, and selected for participation.										
PROCEDURE AND FOLLOW-UP:	All subjects that receive an EchoMark LP will be evaluated at the following time-points: • 15 days (+/- 7 days) • 30 days (+/- 7 days) • 60 days (+/- 15 days) • 90 days (+/- 15 days) • 120 days (+/- 15 days) • 150 days (+/- 15 days) • 150 days (e month) (+/- 15 days) • 12 Month (1 Year) (+/- 15 days) • 15 Months (+/- 15 days) • 18 Months (+/- 15 days) • 24 Months (+/- 15 days) • 24 Months (+/- 15 days) Except for the 180 day (6 month), 12 month (1 year), 15 Month, 18 Month, and 24 Months visits, each visit will include a physical exam, Duplex scan, EchoSure scan, and assessment for adverse events. The monthly EchoSure scans will be suspended after the 120-day (4 month) visit or once radiographic maturation is achieved, whichever is longer, but clinical follow-up and Duplex will continue per the above schedule. The 180-day (6-month) and 12 month (1 year)visits will include a physical examination, Duplex scan for patency, and an assessment for adverse events. The 15 Month, 18 Month, and 24 Month visits will include a physical examination, Duplex scan for patency, and an assessment for adverse events. The 15 Month, 18 Month, and 24 Month visits will include capture of medical history since the last visit, a duplex scan, information on any fluid collection observed on the Duplex scan, and an assessment for any adverse events. EchoSure scans will be completed by study personnel who do not have prior ultrasound training and are representative of non-expert users. Subjects that are consented but do not receive the EchoMark LP will be considered a screen failure, and can be replaced.										
Primary Endpoint	The primary safety and feasibility endpoints are as follows:										
	Primary Safety:										

	 Composite of new major device related adverse events (MAEs) at 30 days post EchoMark LP implantation, as adjudicated by the Clinical Events Committee (CEC), including: Device or procedure-related death Device related infection Device related interventions Device related hospitalizations Fistula failure Fistula rupture Aneurysm 							
	After the close of the final 90-day visit window, all evaluable subjects will be summarized and expansion to a pivotal trial will be requested under a new IDE.							
	Primary Feasibility (Technical Success):							
	Rate of Technical Success defined as the successful implantation of the EchoMark LP implant and the ability to determine blood flow, diameter and depth measurements using the EchoSure diagnostic ultrasound system. Technical success will be assessed from baseline to 4 months.							
OBSERVATIONAL ASSESSMENTS	 The following observational analyses will be performed and/or summarized: Comparison of EchoSure and duplex measurements of flow, diameter, and depth. Only duplex images that pass a quality control check by an independent RVT will be included in the assessment. Comparison of EchoSure depth measurements to Independent Reviewer measured depth results. Time to radiographic maturation is defined as the number of days from baseline procedure to date of radiographic maturation (date of ultrasound imaging, as adjudicated by the CEC). Radiographic maturation is defined as a fistula with volume flow of 500mL/min and 5mm diameter. Time to clinical maturation defined as the number of days from baseline procedure to date of clinical maturation. Clinical maturation is defined as 75% of dialysis sessions with successful 2 needle cannulation. Date of clinical maturation is defined as first date of the 4-week window when clinical maturation is achieved. Radiographic maturation success rate defined as the percentage of subjects that achieve radiographic maturation (as determined by the physician and adjudicated by the CEC) by end of study. 							

Radiographic maturation is defined as a fistula with 500mL/min and 5mm diameter.

- Clinical maturation success rate is defined as the percentage of subjects that achieve clinical maturation by end of study. Date of clinical maturation is defined as first date of the 4-week window when clinical maturation is achieved.
- 6-month patency rate as defined by the status (yes/no) of an arteriovenous dialysis access with detectable blood flow through and beyond the anastomosis shown by either an imaging modality or physical examination (presence of a palpable thrill or audible bruit along some point of the arteriovenous dialysis access beyond the arteriovenous anastomosis).
- 12-month patency rate as defined by the status (yes/no) of an arteriovenous dialysis access with detectable blood flow through and beyond the anastomosis shown by either an imaging modality or physical examination (presence of a palpable thrill or audible bruit along some point of the arteriovenous dialysis access beyond the arteriovenous anastomosis).
- Occurrence of events occurring within 30 days of implantation that require reinterventions (open or endovascular), hospitalizations, or prolongation of existing hospitalization.
- Occurrence of reported reduction of blood flow of blood flow that prevents the ability to cannulate or requires further assessment and/or intervention from baseline procedure to 12 months.
- Occurrence of reported inability to cannulate fistula beginning once the fistula is deemed radiographically and clinically mature to 12 months.
- Occurrence of the development of steal syndrome from baseline to 12 months.
- Occurrence of bleeding requiring surgical intervention (including PRBC transfusion) from baseline to 12 months.
- Occurrence of infiltration requiring procedural intervention from baseline to 12 months.
- Occurrence of hematoma requiring procedural intervention from baseline to 12 months.
- Occurrence of the inability to use the EchoSure component of the system, from baseline to 4 months, due to:
 - Migration of the EchoMark device
 - Early resorption of the EchoMark device as defined as breakdown of the EchoMark shape prior to 4 months from index procedure.
- Occurrence of pain related to the study devices from baseline to 12 months.
- Occurrence of infection (not limited to infection requiring implant explantation) from baseline to 12 months.

	 Occurrence of infection confirmed by either implant explantation or purulent fluid on pathologic assessment during incision and drainage beginning at baseline to 12 months. Composite of new major device related adverse events (MAEs) at 12 months post EchoMark LP implantation, as adjudicated by the Clinical Events Committee (CEC). The proportion of subjects with device success and free from device- and/or procedure-related SAEs (per CEC adjudication) at 12 months. The summaries for each individual safety data point will also be provided, including: Device or procedure-related death Device related infection Device related hospitalizations Fistula failure Fistula rupture Aneurysm
Oversight	A Data Safety Monitoring Board (DSMB) will be employed to provide safety oversight. A Clinical Events Committee (CEC) will be employed to provide adjudication of endpoints. An Independent RVT will be employed to adjudicate and perform a quality check of Duplex imaging. The Independent RVT will not review any measurements from the EchoSure system.
INCLUSION CRITERIA	 Males or non-pregnant, non-breastfeeding females ≥ 18 years of age but < 85 years of age at the time of informed consent Subject is able and willing to provide written informed consent prior to receiving any non-standard of care, protocol specific procedures Subject is willing and capable of complying with all required follow-up visits Subject and/or Care Team agree that the distance and transportation resources from the subject's home to the clinic are reasonable for study participation and compliance Subject is ambulatory (cane or walker are acceptable) Subjects presenting for upper arm autologous arteriovenous fistula creation Vein diameter > 2.5 mm at the antecubital fossa via imaging Artery diameter > 3 mm via imaging Subject is not participating in another investigational clinical trial that has not met its primary endpoint. Participation in a post- market registry is acceptable.

Exclusion Criteria	 Subject is receiving a forearm fistula. Subject has history of Steal Syndrome Subject who is immunocompromised or immunosuppressed Subject has had three previous failed AV fistulae for hemodialysis access
	5. Subjects expecting to undergo major surgery within 60 days from the EchoMark LP implantation.
	6. Known or suspected active infection on the day of the index procedure.
	7. Subjects who had infection(s) in the 30-day window prior to EchoMark placement to reduce the likelihood of partially treated infections that can seed the device and fistula.
	 Subjects with diagnosed bleeding disorder, thrombocytopenia (platelet count <50,000), hypercoagulability, and history of recurrent deep vein thrombosis not related to AV access.
	9. Subjects with active malignancy.
	10. Subjects with a history of poor compliance with the dialysis protocol.
	11. Subjects with a known or suspected allergy to any of the device materials.
	12. Subjects with an existing fistula or graft.
	13. Subjects who are pregnant, plan to become pregnant, or are breastfeeding.

Table 1: Schedule of Events

				Follow-Up at Vascular Surgeon Office/Clinic										
Study Requirement	Screening / Enrollment	Index Procedure	Discharge	15 days ±7 Days	30 Days ±7 Days	60 Days ±15 Days	90 Days ±15 Days	120 Days ±15 Days	150 Days ±15 Days	180 Days ±15 Days	12 Month ±15 Days	15 Month ±15 Days	18 Months ±15 Days	24 Months ±15 Days
Informed Consent	x													
Inclusion / Exclusion Criteria	x													
Blood Culture for Bacteremia	x													
Demographics	х													
Medical History and Most Recent Kt/V, CBC, Serum chemistry, Calcium, Phosphorous, Magnesium, Total Protein, Albumin, PTH	х			х	х	х	х	х	х	х	х	х	х	х
Relevant Medications	x			х	х	Х	х	х	x	х	х	х	х	X
Physical Examination / Vital Signs	х	х	х	х	x	х	x	x	x	х	х			
Fistula Creation		x												
EchoMark LP Implantation		x												

Sonavex, Inc.	EchoMark/EchoSure System Feasibility Study Synopsis													
External EchoMark Measurements			Х	Х	х	Х	Х	Х	Х	Х	Х			
Duplex Scans	Х		Х	Х	Х	Х	Х	Х	Х	Х	Х	Х	Х	Х
EchoSure Scans*			X	Х	Х	Х	Х	Х	X					
Cannulation Log, including attempts				Х	Х	Х	Х	Х	х	Х	Х			
AE Monitoring		Х	X	Х	Х	Х	Х	Х	Х	Х	Х	Х	Х	Х
End of Study														Х

** Note: The monthly EchoSure scans will be suspended after the 120 day (4 month) visit or once radiographic maturation is achieved, whichever is longer. Patients will continue to be followed monthly with physical examination, Duplex, and AE monitoring until the 180-day timepoint. If radiographic maturation is never achieved, patients will be followed until either the fistula is abandoned, or the patient reaches the 180-day timepoint. The 180-day timepoint is meant to assess patency via Duplex and is meant for AE monitoring.

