7.7 Post-Maturation Follow-up at 150 Days if Radiographic Mature

The EchoSure scans will be suspended after the 120 day (4 month) visit or once radiographic maturation is achieved, whichever is longer. Radiographic maturation is defined as fistula diameter \geq 5mm, fistula flow \geq 500 mL/min. If radiographic maturation has been achieved before the 150-day follow-up visit, the subject will not switch to the Post Maturation follow-up schedule until the 150 Day visit when the EchoSure scans are suspended. Post-Maturation follow-up visits will include a physical exam, medical history review, Duplex scan, external EchoMark measurement, and adverse event monitoring. The physical exam will include assessing the fistula for bruit and thrill. The medical history will include all interventions, cannulation attempts, and the most recent Kt/V, CBC, Serum Chemistry, Calcium, Phosphorous, Magnesium, Total Protein, Albumin, PTH, Duplex scans will include:

• Assessment of patency (flow/no flow adjudicated by the CEC)

- Limited DUS scan performed at the site of EchoMark to determine EchoMark visibility including:
 - o 1 BMode, transverse view of EchoMark at center
 - o 1 BMode, transverse view of EchoMark at distal edge
 - o 1 BMode, Transverse view of EchoMark at proximal edge
 - 1 BMode, Longitudinal view centered over vessel showing full length of EchoMark
- A duplex exam of the fistula from the EchoMark location and beyond to assess for the presence of stenotic lesions. If a lesion is present, capture and save an image showing a longitudinal view of the fistula segment with the stenosis, note the location of the stenosis in relation to the anastomosis and EchoMark, and track the stenosis as an adverse event.
- A duplex scan of the brachial artery to assess flow and diameter, capture a PW image showing the flow and diameter measurements.

7.8 180 Day and 12 Month (+ 15 Days) Follow-up

All subjects will have follow-up visit at 180 days and 12 months after baseline procedure. Follow-up visits will include a physical exam, medical history review, Duplex scan, external EchoMark measurement, and adverse event monitoring. The physical exam will include assessing the fistula for bruit and thrill. The medical history will include all interventions, cannulation attempts, and the most recent Kt/V, CBC, Serum Chemistry, Calcium, Phosphorous, Magnesium, Total Protein, Albumin, PTH, Duplex scans will include:

- Assessment of patency (flow/no flow adjudicated by the CEC)

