- Limited DUS scan performed at the site of EchoMark to determine EchoMark visibility including:
 - 1 BMode, transverse view of EchoMark at center
 - 1 BMode, transverse view of EchoMark at distal edge
 - 1 BMode, Transverse view of EchoMark at proximal edge
 - 1 BMode, Longitudinal view centered over vessel showing full length of EchoMark.
- A duplex exam of the fistula from the EchoMark location and beyond to assess for the presence of stenotic lesions or a fluid collection. If a lesion is present, capture and save an image showing a longitudinal view of the fistula segment with the stenosis, note the location of the stenosis in relation to the anastomosis and EchoMark, and track the stenosis as an adverse event. If a fluid collection is present, capture and save an image noting the location from the anastomosis and the size and volume.
- A duplex scan of the brachial artery to assess flow and diameter, capture a PW image showing the flow and diameter measurements.

7.9 15 Month, 18 Month, and 24 Month (+ 15 Days) Follow-up

All subjects who are willing to reconsent to longer-term follow-up will have a follow-up visit at 15 months, 18 months, and 24 months after baseline procedure. Follow-up visits will include a captures of medical history since the last visit, Duplex scan, and adverse event monitoring. The Duplex scans will include:

- Limited DUS scan performed at the site of EchoMark to determine EchoMark visibility including:
 - 1 BMode, transverse view of EchoMark at center
 - 1 BMode, transverse view of EchoMark at distal edge
 - o 1 BMode, Transverse view of EchoMark at proximal edge
 - 1 BMode, Longitudinal view centered over vessel showing full length of EchoMark
- A duplex exam of the fistula from the EchoMark location and beyond to assess for the presence of a fluid collection. If a fluid collection is present, capture and save an image noting the location from the anastomosis and the size and volume.

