7.11 Fistula Failure

If the subject's fistula is deemed a failure and abandoned by the investigator, a fistula failure case report form will be completed recording the reasoning for the failure. The subject will remain in the study and receive monthly telephone calls to monitor for adverse events and physical assessments of the EchoMark at all standard of care visits. The subject will complete the 180-day and 12 months visit as scheduled to undergo a physical exam, medical history review, adverse event monitoring, and duplex examination of the EchoMark and exit the study.

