11. STATISTICAL ANALYSIS

11.1. Sample Size Considerations

This is a feasibility study and accordingly there is not a pre-specified null hypothesis to be tested against for the study endpoints. Data collected from this study will provide preliminary device safety and effectiveness data for the use of the EchoMark/EchoSure System in patients receiving arteriovenous fistulae for hemodialysis access. Descriptive statistics will be reported for the study data. Inferential statistical analysis will be conducted in an exploratory manner. The sample size for this study is planned to be up to 20 subjects at up to 4 investigational sites, with data points collected at multiple timepoints for each subject.

Statistical methods for the study are outlined below.

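### The Table 1 note and sections 7.8, 7.9 and 7.11 set conflicting ends of follow-up for never-mature and abandoned fistulae, so 12-month safety data could be lost selectively in poor-outcome subjects

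*Combined protocol and SAP*

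**What the plan says.** Several places set or imply an end of follow-up.

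- **Table 1, note.** On monthly visits: "Patients will continue to be followed monthly with physical examination, Duplex, and AE monitoring until the 180-day timepoint". The next sentence covers fistulae that never mature: "If radiographic maturation is never achieved, patients will be followed until either the fistula is abandoned, or the patient reaches the 180-day timepoint".
- **Section 7.8.** "All subjects will have follow-up visit at 180 days and 12 months after baseline procedure". No exception is made for never-mature or abandoned fistulae.
- **Section 7.11, failed and abandoned fistula.** "The subject will remain in the study and receive monthly telephone calls to monitor for adverse events". Then: "The subject will complete the 180-day and 12 months visit as scheduled to undergo a physical exam". The same sentence ends with exit from the study.
- **Section 7.9.** "All subjects who are willing to reconsent to longer-term follow-up will have a follow-up visit at" 15, 18 and 24 months. These visits look for fluid collections, and fistula status does not restrict them.
- **Synopsis, 5.3 and Table 1.** The synopsis gives enrollment of up to 365 days, but lists visits to 24 months for every implanted subject without mentioning reconsent. Section 5.3 caps participation at 24 months. Table 1 marks End of Study at 24 months.

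On the analysis side, the sample is all enrolled subjects with successful implantation (11.2.4). The MAE composite and most event counts run to 12 months (11.2.8.10, 11.2.8.11). Missing values are not imputed (11.2.10). Section 4.2.3 defines 12-month patency without restriction, whereas 11.2.8.8 makes it conditional on both radiographic and clinical maturation.

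**The concern.** Read literally, the note ends follow-up because of a poor outcome: the fistula was abandoned, or it had not matured by day 180. Such subjects may still carry the implant, and they belong to the sample in which 12-month safety is reported. If a site stops there, later infections, interventions, hospitalizations and pain are unobserved in a group selected by outcome, and the analysis has no means of making up the loss.

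The second conflict comes later. A failed-fistula subject who exits at 12 months under 7.11 misses the fluid-collection surveillance that 7.9 offers to everyone who reconsents. The protocol's risk section records infection and seroma in earlier use in this population, so late safety observation matters to the study's purpose.

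**Working it through.** The plan states no figure on this point. It is a descriptive study in which "there is not a pre-specified null hypothesis to be tested against for the study endpoints", so no power or error-rate calculation applies. The check is a comparison of texts, followed by a sizing.

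**Step 1: the rules side by side**

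| Subject | Table 1 note | 7.8 | 7.11 | 7.9 |
|---|---|---|---|---|
| Never mature, abandoned | ends at abandonment (day 180 at latest) | 180 days and 12 months | stays to 12 months, then exits | 15–24 months on reconsent |
| Never mature, not abandoned | ends at day 180 | 180 days and 12 months | does not apply | 15–24 months on reconsent |

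The first row holds two conflicts: the note against 7.8 and 7.11 up to 12 months, and 7.11 against 7.9 after 12 months. The second row holds one: the note against 7.8, and with it 7.9.

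**Step 2: how many subjects**

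Inputs: N = 20 ("The sample size for this study is planned to be up to 20 subjects", roll-ins extra), and failure rates from the outcomes table in section 3.5. Those rates are 11.8% (all 34 prior patients), 16.7% (the 30 with an assigned outcome or more than 90 days post-surgery) and 28% to 36% (the tabulated literature cohorts). As a check on the second rate, 25 mature of 30 gives an exact 95% interval of 65.3% to 94.4%, which matches the interval printed in 3.5. The failure share is therefore 5/30 = 16.7%.

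Expected number affected = 20 × failure rate:

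- 20 × 0.118 = 2.4
- 20 × 0.167 = 3.3
- 20 × 0.28 = 5.6
- 20 × 0.36 = 7.2

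The chance of at least one, 1 − (1 − rate)^20, is 92% at 11.8% and 97% at 16.7%.

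**Step 3: what would go unseen**

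Take a single late event type, such as infection after day 180, with no case among the subjects still observed. If k subjects are unobserved, the proportion over all 20 could lie anywhere from 0 to k/20:

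- k = 2: 0% to 10%
- k = 3: 0% to 15%
- k = 7: 0% to 35%

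The endpoints in 11.2.8.10 are total numbers of events. For them, lost follow-up lowers the count itself and does not show as a smaller denominator.

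**Step 4: which endpoints are exposed**

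- *MAE composite (11.2.8.11).* Fistula failure is a component, so a subject adjudicated as failed already has an event. The exposure is in the other components reported singly, and in never-mature subjects not yet declared failures when observation stops.
- *Event counts (11.2.8.10).* Exposed for all affected subjects, except the items that end at 4 months or begin only at maturity.
- *12-month patency.* Under 11.2.8.8, never-mature subjects fall outside the rate whatever their follow-up. A gap arises only under 4.2.3. Section 7.11 lists a Duplex examination of the EchoMark but not the patency assessment listed in 7.8, although its physical exam could supply patency.

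**The case against.** The strongest reply is that the note governs monthly visits only. It annotates the EchoSure scan row, and its preceding sentence concerns monthly follow-up. Taken as an end-of-study rule, that preceding sentence would also stop matured subjects at day 180, against the table it annotates. Section 7.11 fits this reading, since telephone calls replace visits after abandonment. Table 1 itself marks Duplex and adverse-event monitoring through 24 months without exception. On this view 12-month safety data are lost only if a site places one sentence of a note above two explicit sections.

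Much of this stands. The benign reading is plausible, and the loss is conditional on the note being followed. But the sentence speaks of following patients, not of monthly visits, and it sits under the schedule that sites work from. The benign reading also leaves the exit in 7.11 at odds with 7.9.

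A reader might go further and count three contradictory ends of study: day 180, 12 months and 24 months. The documents do not support that. Twenty-four months is a cap in 5.3, and under 7.9 the late visits depend on reconsent; a 12-month base with an optional extension is not in itself a contradiction. The narrower conflict is that 7.11 closes an extension which 7.9 leaves open.

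**Conclusion.** The conflict is in the text and worth correcting. The note disagrees with 7.8 and 7.11 on follow-up to 12 months, and 7.11 disagrees with 7.9 on follow-up after it. If the note is applied literally, about 2 to 3 of 20 subjects would be affected at the sponsor's prior rates, and up to about 7 at 36%. This assumes full enrollment of 20, and that failure to mature in those cohorts is a fair stand-in for never-mature or abandoned fistulae here. If sites follow 7.8 and 7.11, the loss before 12 months does not occur.

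Three stronger inferences are not supported:

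- *That the 12-month MAE composite would be computed mainly in successes.* Adjudicated failures already count as events, so removing failures from an event-free denominator does not describe the composite.
- *That the 14.7% with outcome not yet known should be added to the failures.* Section 3.5 describes them as undetermined or not yet communicated, and expects that many may become successes.
- *That every abandoned fistula is a patency failure.* Both patency definitions rest on detectable flow, which an abandoned fistula may still have.

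The endpoints concerned are observational and descriptive. The importance lies in selective loss of safety information, not in any test or decision threshold.

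**What to change.** 1. **Protocol.** Reconcile the Table 1 note with 7.8, 7.9 and 7.11, and with the synopsis and 5.3, so that one end-of-follow-up rule applies to never-mature and abandoned-fistula subjects. State whether the limit of abandonment or day 180 covers only the monthly visits. State whether failed-fistula subjects may reconsent to the visits after 12 months. The choice of rule is the sponsor's; the 12-month endpoints should be worded to match it.
2. **Section 11.2.8.11.** State that the 12-month MAE denominator is all implanted subjects, with CEC-adjudicated fistula failures counted as events.
3. **Sections 4.2.3 and 11.2.8.8.** Give one population for 12-month patency, unrestricted or conditional on maturation. Keep the detectable-flow definition; do not score abandoned fistulae automatically as not patent.

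The cost is a protocol clarification and a few sentences of analysis wording. Depending on the rule chosen, it may add a few visits for a few subjects, all of a kind already described in 7.8, 7.9 and 7.11. The sample size does not change.
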